# 9 STATISTICAL CONSIDERATIONS

#### 9.1 Sample size

The sample size for this trial will be adaptively determined through a phase 2/3 design. Enrollment is planned to last approximately 2 months. Each patient will be randomly allocated to Reparixin or Control according to a randomization ratio of 2:1 and he/she will be followed for the entire treatment and follow-up duration for collecting the efficacy endpoints of each study phase.

For the Phase 2 portion of the study, the primary analysis will compare Reparixin versus Control in terms of time to a composite endpoint (primary endpoint of phase 2) including the following events: requirement of supplemental oxygen treatment, mechanical ventilation use, admission to ICU, and any requirement of rescue medication. Based on clinical experience, an improvement of the median time freedom from composite event of 1.5 times is expected. Assuming an exponential distribution, a total sample size of 48 patients will allow to provide 80% power to show superiority of Reparixin compared to control using a log-rank test at a one-sided significance level of 0.025.

The sample size for the phase 3 is based on assessment of superiority of Reparixin compared to control arm in terms of freedom from a composite endpoint (primary endpoint of phase 3) of severe events including death, admission to the ICU, requirement of mechanical ventilation.

Based on same assumptions of phase 2 regarding randomization (2:1) and expecting to double the median time freedom from severe composite event using Reparixin compared to control (from 2-4 to 4-8 days), a total sample size of 111 patients will allow to achieve a power of 90% to show superiority of Reparixin over control using a log-rank test at a one-sided significance level of 0.025. No drop-out are expected to happen. The number of patients to be included may be revised based on considerations from Phase 2 data analysis.

Primary endpoint of phase 3 will be tested only if superiority of Reparixin is shown in phase 2. Thus, the overall type I error of the study will be controlled at 0.025 via the hierarchical testing procedure.

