3.2 Sample size justification

The sample size of the full phase 2/3 study is calculated based on data from clinical experience and on Sponsor expectations as reported in Table 2:

Table 2: Assumptions for primary endpoints

Primary endpoint*	Standard of care (control)	Reparixin
Time to primary endpoint of phase 2	2 days	5 days
Time to primary endpoint of phase 3	2-4 days	4-8 days

* see section 3.5.1.

Based on the following assumptions:

- an enrollment phase of 2 months,

- a total follow-up of 21 days,
- a randomization ratio (reparixin:control) of 2:1
- an exponential distribution for survival probability $S(t) = e^{-\lambda t}$,
- a comparison between treatment by means of a log-rank test,
- an interim analysis framework as described in section 4.5, and
- a correction of the type I and II errors by means of O'Brien-Fleming spending functions

a total of 109 events (corresponding to approximately 111 subjects) will allow to provide >80% power to show superiority of reparixin vs standard of care in terms of primary endpoint of phase 3, controlling the type I error under 0.025.

Based on the same assumptions reported above, phase 2 portion of the study will be performed when a total of 46 events (corresponding to approximately 48 subjects) has happened. This allow to achieve approximately 80% power to show superiority of reparixin vs standard of care in terms of (not severe) primary endpoint of phase 2, controlling the type I error under 0.025.

The remaining portion of the 111 patients will be enrolled in the phase 3 study segment. Anyhow, due to the novel nature of the COVID-19 pandemic and being the primary efficacy endpoint planned in phase 3 not well established, it may require confirmation based on phase 2 data. For this reason, at the end of the phase 2 portion, power calculations may be reassessed, and sample size may be re-estimated for phase 3.

The adaptive design allows for the assessment of efficacy endpoint in phase 2 which are then seamlessly confirmed in the phase 3. Since primary endpoint of phase 3 will be tested only if superiority of reparixin is shown in phase 2 (at interim or final stage), the overall type I error of the study will be controlled at 0.025 via the hierarchical testing procedure.

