7.1.3 Sensitivity analysis

7.1.3.1 Phase 2

Results of primary analysis will be assessed in sensitivity analyses as detailed below.

- The comparison between treatment and control will be performed by means of a Cox regression model, using age class, gender and clinical severity score at baseline as covariates, to assess the robustness of results on primary endpoint versus the presence of confounding factors. Additional covariates might be included after DRM in case relevant baseline imbalance will be identified between groups, despite randomization. The assumptions of proportionality will be investigated with a time-dependent exploratory variable, which is defined as $\text{treatment} * \{\log[\text{time to event}]\}$. If the p-value from the Wald Chi-squared statistic for this variable is less than 5% there is evidence of a departure from the adjusted model assumptions. In case of non-proportional hazards, a Weibull model will be assumed as parametric form of the distribution of survival times. The treatment group will be included in the model as covariate.
- Time to event for each single component of the primary endpoint will be performed separately in order to adjust for the presence of possible competing risks. The following events:
 - first supplemental oxygen requirement,
 - first mechanical ventilation use,
 - first admission to ICU, and
 - first use of a rescue medication for any reason

will be analyzed according to survival analysis methodology detailed in section 4.1 with the following modifications:

- the common representation of survival curves using the Kaplan-Meier estimator will be replaced by the cumulative incidence function,
- the presence of other competing event(s) is/are treated as censored.
- A modified composite endpoint of phase 2 will be analyzed adding “death” as fifth component. It will be analyzed according to section 7.1.2 to assess the robustness of results on primary endpoint versus the presence of censoring due to fatal events.

Decision to proceed/not proceed to phase 3 will be based only on primary analysis results, despite inconsistencies with sensitivity analyses. Sensitivity results will be interpreted and discussed in the clinical study report and will be used to eventually adjust adaptations for the phase 3.

7.1.3.2 Phase 3

Results of primary analysis will be assessed in sensitivity analyses as detailed below.

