- The comparison between treatment and control will be performed by means of a regression model, using the same method (Cox or Weibull model) and covariates identified during phase 2, to assess the robustness of results on primary endpoint versus the presence of confounding factors.
- Time to event for each single component of the severe primary endpoint will be performed separately in order to adjust for the presence of possible competing risks. The following events:
 - death,
 - first invasive mechanical ventilation use, and
 - first admission to ICU

will be analyzed according to survival analysis methodology detailed in section 4.1 with the following modifications:

- the common representation of survival curves using the Kaplan-Meier estimator will be replaced by the cumulative incidence function,
- the presence of other competing event(s) is/are treated as censored.
- The comparison between treatment and control will be performed in the PP population instead of FAS as described in section 7.1.2, to assess the robustness of trial results versus the adherence to protocol.

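### The SAP's Weibull fallback for non-proportional hazards itself assumes proportional hazards, and the phase 2 model choice passes to a different phase 3 composite without a new check

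*SAP*

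**What the plan says.** SAP 7.1.3.1 (phase 2) plans a Cox model adjusted for age class, gender and baseline clinical severity score. Its stated aim is robustness against confounding. Proportionality is tested with a treatment by log(time) term, and a Wald p-value below 5% counts as evidence of departure. The SAP then says: "In case of non-proportional hazards, a Weibull model will be assumed as parametric form of the distribution of survival times". The next sentence is: "The treatment group will be included in the model as covariate". The section mentions no arm-specific shape, stratification, time-varying effect, restricted mean or weighted test.

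SAP 7.1.3.2 (phase 3) repeats the regression "using the same method (Cox or Weibull model) and covariates identified during phase 2". It states no fresh proportionality check. The two composites in SAP 3.5.1 differ: phase 3 adds death and drops supplemental oxygen and rescue medication.

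The primary analysis in both phases is Kaplan-Meier with a one-sided log-rank test (SAP 7.1.2). SAP 7.1.3.1 rests the decision on phase 3 on that analysis alone, but lets sensitivity results inform phase 3 adaptations. Protocol 9.4.2.4 names only Cox regression.

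**The concern.** A fallback should relax the assumption that failed. This one keeps it and adds a second, a parametric baseline hazard. If the check rejects proportional hazards, the adjusted sensitivity result is still one constant treatment effect, now under a different model name.

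The branch is not far-fetched in phase 2. Protocol 6.1 plans 7 days of treatment, prolonged up to 21 days only in patients who improve, while SAP 3.2 follows events for 21 days. A treatment effect that changes over time is therefore plausible. A reader of the study report could take agreement between the Weibull and log-rank results as reassurance about non-proportionality, which it would not be. The phase 2 model choice would also govern an endpoint on which proportionality had not been examined.

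**Working it through.** **Inputs from the documents.** Allocation is 2:1, follow-up is 21 days and survival is exponential (SAP 3.2). Phase 2 has 46 events in about 48 patients, with assumed times of 2 and 5 days ("Time to primary endpoint of phase 2 2 days 5 days"). Phase 3 has 109 events in about 111 patients, with 2-4 against 4-8 days. The primary test is a "log-rank test at a one-sided significance level of 0.025" (Protocol 9.1).

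**The plan's own figures.** The plan gives no figure for the fallback, so the design figures were reproduced first.

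- Phase 2: the hazard ratio is 2/5 = 0.40. z = √(46 × 2/9) × ln(2.5) − 1.960 = 3.197 × 0.916 − 1.960 = 0.970, a fixed-design power of 83.4%. With the SAP Table 4 boundaries, simulated power is 80.1% with futility applied and 83.1% without. The SAP says: "This allow to achieve approximately 80% power to show superiority of reparixin vs standard of care". This reproduces.
- Phase 3: the hazard ratio is 0.50. z = √(109 × 2/9) × ln(2) − 1.960 = 4.922 × 0.693 − 1.960 = 1.451, or 92.7%. With the SAP Table 5 boundaries and futility it is 90.3%. This agrees with Protocol 9.1 ("a total sample size of 111 patients will allow to achieve a power of 90" per cent).

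Protocol 9.1 also states for phase 2 that "an improvement of the median time freedom from composite event of 1.5 times is expected". That differs from the SAP's 2 against 5 days and is a separate matter.

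**Algebra of the fallback.** With one shape k and treatment x as covariate, h(t|x) = k·t^(k−1)·exp(−k(b0 + b1·x)). Therefore h(t|1)/h(t|0) = exp(−k·b1) for every t. Reporting a time ratio exp(b1) does not escape this, because the hazard ratio is the time ratio raised to the power −k. With arm-specific shapes k1 and k0 the ratio is proportional to t^(k1−k0) and can change with time.

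**Numerical illustration.** The scenarios are assumptions made here. All use 2:1 allocation and censoring at day 21. The first three have a control median of 4 days and 120,000 simulated patients each. The last two have a control median of 2 days and 9,000 patients.

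| True hazard ratio | Cox | Weibull, common shape | Difference |
|---|---|---|---|
| 0.3 to day 3, then 1.5 | 0.97 | 0.99 | 0.02 |
| 0.4 to day 7, then 1.0 | 0.58-0.59 (two runs) | 0.59 | 0.01 or less |
| 1.0 to day 3, then 0.3 | 0.56 | 0.54 | 0.02 |
| 0.2 to day 3, then 1.5 | 0.6351 | 0.6412 | 0.006 |
| Shape 1.0 control, 0.6 reparixin | 0.4096 | 0.3944 | 0.015 |

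In the last two rows the common-shape Weibull ratio was identical at days 0.5, 2, 5, 10 and 20. For the fourth row k = 1.480 and the time ratio is 1.350, and 1.350^(−1.480) = 0.641, as the algebra requires. Freeing the shape by arm released the ratio over days 0.5 to 20: from 0.127 to 4.53 in the fourth row and from 0.611 to 0.134 in the fifth. The value 4.53 against a true late ratio of 1.5 also shows a limit: an arm-specific shape gives the direction of change but forces a smooth power of time.

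**How often the branch would be entered.** The 5% check was simulated without covariates at 48 patients, 2:1, control median 4 days, 600 runs per scenario. It triggered in about 37%, 12% and 28% of runs for the first three rows.

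**The case against.** The strongest reply is that little depends on this. It is one branch of one sensitivity analysis, and at 48 patients the branch is entered in only about 12 to 37% of runs even when hazards are clearly non-proportional. The log-rank test, boundaries and decision rule do not use it. The time pattern is not wholly hidden either, because Kaplan-Meier curves with numbers at risk and event rates by time point are planned (SAP 4.1 and 7.1.2). The analysis aims at confounding, not at describing effect over time. Fixing the phase 3 model before phase 3 data arrive avoids data-driven model choice, and SAP 4.7 and 7 foresee amendment before phase 3.

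Most of this stands, and it limits the weight of the point. It does not rescue the rule: the SAP names the Weibull model as its response to non-proportional hazards, and as specified the model cannot serve that purpose. Pre-specifying the phase 3 analysis is sound, but it does not require carrying over a choice triggered by a test on another composite.

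Three stronger readings are not supported:

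- A reader might infer that the phase 2 or phase 3 conclusion is compromised. SAP 7.1.3.1 excludes that for the decision to proceed, and alpha and power do not involve this model.
- A reader might infer that phase 3 will use Weibull. It does so only if the phase 2 check triggers and the text is not amended.
- A reader might infer that the fallback is literally the same analysis. It shares the proportional-hazards assumption but adds a parametric baseline.

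**Conclusion.** The rule is wrong as written. With the single common shape that the SAP's wording implies, the fallback imposes the constant hazard ratio that its trigger has rejected, and in the five scenarios it changed the estimate by about 0.02 or less. The algebra needs no assumption beyond that common shape; an arm-specific shape would answer the criticism, but none is specified. The scenario figures rest on assumed hazard patterns and only illustrate size. The argument from the 7-day course applies to phase 2, since Protocol 6.1 leaves phase 3 treatment duration open.

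The consequence is limited to a conditional sensitivity analysis and to what it may contribute to phase 3 adaptations. The change is worth making because the present text could give false reassurance and the correction is cheap.

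**What to change.** In SAP 7.1.3.1, replace the Weibull fallback with a method that does not assume proportional hazards and keeps the planned covariates. One choice is the covariate-adjusted difference in restricted mean event-free time to day 21 with 95% CI, with a stated rule if observation in either arm ends earlier. Alongside it, report the adjusted Cox model with the treatment by log(time) term retained, or a Weibull model with arm-specific shape, to show how the effect changes.

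An unadjusted restricted mean would lose the adjustment that is the purpose of this analysis. A Cox model split at day 7 is not a good substitute in phase 2: with 16 controls and a 2-day median, 16 × 2^(−7/2) = 1.4 are expected to be event-free at day 7. In phase 3 at the same median it is 37 × 2^(−7/2) = 3.3.

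In SAP 7.1.3.2, apply the same pre-specified analyses and the proportionality check to the phase 3 endpoint, and delete the carry-over of the model chosen in phase 2.

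The cost is SAP wording and a little more analysis, with no new data. Intervals will be wide at 48 patients.

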3.5 Efficacy endpoints

3.5.1 Primary endpoints

- Primary Endpoint for phase 2: Composite endpoint of clinical events (the subject requires at least one of the following: supplemental oxygen requirement, invasive mechanical ventilation use, admission to ICU, and use of a rescue medication for any reason);
- Primary Endpoint for phase 3: Composite endpoint of death and clinical severe events (the subject dies or requires invasive mechanical ventilation use and/or admission to ICU).

3.5.2 Secondary Endpoints:

- Clinical severity score (a seven-category ordinal scale) at any available time point
- Dyspnea severity (Liker categorical scale and VAS continuous scale) at any available time point;
- Changes in body temperature at any available time point;
- Duration and quantity of supplemental oxygen treatment at any available time point;
- Incidence and duration of mechanical ventilation use at any available time point;
- Incidence of ICU admission need at any available time point;
- Lung damage extension changes from baseline (assessed by Chest CT or Rx) at any available time point;
- Change from baseline in lung exudation degree (assessed by Chest CT or Rx) at any available time point;
- PaO₂ at any available time point;
- SpO₂ at any available time point;
- Partial arteriolar oxygen pressure (PaO₂) to fraction of inspiration O₂ (FiO₂) ratio at any available time point;
- CRP at any available time point;
- Hs-CRP at any available time point;

3.5.3 Exploratory Endpoints (not mandatory):

- Cytokine profile at any available time point;

- Concentration of reparixin in serum over time;
- SARS-CoV-2 virologic counts at any available time point.

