4.1 General

Appropriate descriptive statistics will be produced, according to the variable:

- for continuous data n , mean, standard deviation (SD), median, Q1-Q3, and range (minimum and maximum) will be presented;
- for categorical data, frequency distributions and percentages will be presented;
- for time-to-event variables, cumulative freedom from event will be evaluated using Kaplan-Meier (KM) method. The degree of uncertainty will be expressed with 95% confidence limits (calculated per the method proposed by Greenwood³). Comparison of curves among arms will be performed with the log-rank test. KM graphs will be presented along with the number of subject-at-risk at exact time points. Subjects who have discontinued/terminated the study without an event will be censored at the date of study discontinuation/termination. Subjects ongoing and who are free from event at the time of database lock (for example at interim analyses) will be censored at the last available date.

Unless otherwise specified, hypothesis testing will be carried out at the $\alpha = 0.050$ level (two-sided) when comparing treatments. For all inferential analyses, p-value will be rounded to three decimal places. Statistical significance will be declared if the rounded p-value will be less than or equal to 0.050. For primary analysis only (section 7.1.2), p-values will be provided at 5th decimal place, in order to compare with efficacy and futility thresholds specified in section 4.5.

Additional post-hoc analysis may be produced to further allow comparison between reparixin and control, according to the results obtained. Any unplanned analyses as well as deviations from the original statistical plan will be clearly documented in the Clinical Study Report.

Derivation rules for efficacy and safety analyses are reported in Table 7 in section 9.

All the data collected and derived in the study will be presented in subject data listings by centre.

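### A death before any of the four phase 2 components is recorded is censored as event-free, and the SAP keeps the death-included analysis out of the decision to open phase 3

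*SAP*

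**What the plan says.** SAP 3.5.1 lists the phase 2 components as "supplemental oxygen requirement, invasive mechanical ventilation use, admission to ICU, and use of a rescue medication for any reason". SAP 4.9 and Table 7 turn the oxygen component into a fall in PaO2/FiO2 of at least one third from baseline. Table 7 scores the rescue component from eligibility to switch, and uses the visit date if no rescue start date exists. Protocol sections 3 and 9.4.2.1 also leave death out of the phase 2 composite.

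For patients without an event, SAP 4.1 says: "Subjects who have discontinued/terminated the study without an event will be censored at the date of study discontinuation/termination". Table 7 dates a patient with no component at the last date on which all components are known to be absent. Under either rule, a patient who dies with no component recorded is censored.

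The SAP sees this. Section 7.1.3.1 adds death as a fifth component in a sensitivity analysis, "to assess the robustness of results on primary endpoint versus the presence of censoring due to fatal events". It then fixes the gate: "Decision to proceed/not proceed to phase 3 will be based only on primary analysis results, despite inconsistencies with sensitivity analyses". The next sentence allows sensitivity results to be discussed in the study report and to shape phase 3 adaptations. The phase 3 primary composite (SAP 3.5.1, Table 7) does count death.

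**The concern.** The patients are hospitalised with severe COVID-19 pneumonia, aged up to 90, and Protocol 2.1 describes rapid progression to critical disease. Some may die before a component is captured:

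- Table 7 dates ICU admission and PaO2/FiO2 worsening by visit. The scheduled post-baseline visits are Day 1, Day 2, Week 1, end of treatment and end of follow-up.
- Non-invasive ventilation does not meet the ventilation component.
- Rescue is offered only after the first 24 hours.

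A patient who deteriorates and dies between Day 2 and Week 1 could therefore leave no event.

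The log-rank test assumes that a censored patient had the same future risk as those still under observation. That is hard to defend for a patient who has just died of the disease under study. If these deaths are commoner on one arm and stand in for events that would have been counted, that arm looks better than it is. The phase 2 result opens phase 3, and the two stages of one testing hierarchy treat death differently. The analysis that would reveal the problem has no say in the decision.

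**Working it through.** **Reproducing the plan's figure.** Inputs from SAP 3.2: "Time to primary endpoint of phase 2 2 days 5 days" for control and reparixin, exponential times, 2:1 allocation, 21 days of follow-up, 46 events from about 48 subjects, "controlling the type I error under 0.025". Protocol 9.1 gives the sidedness: "using a log-rank test at a one-sided significance level of 0.025".

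- Hazard ratio, reading the times as medians: 2/5 = 0.40.
- Schoenfeld events for 80% power in a fixed design: (1.960 + 0.842)² / [(2/3)(1/3)(ln 0.40)²] = 7.85 / 0.187 = 42.1, so 43. With 46 events, fixed-design power is 83.4%.
- With the SAP Table 4 boundaries (efficacy 0.00258 at 23 events and 0.02400 at 46; futility 0.23349), overall one-sided alpha is 0.0250. Power is 83.1% if futility is ignored and 80.1% if it is followed.
- Expected events by day 21: 16(1 − 2^(−21/2)) + 32(1 − 2^(−21/5)) = 15.99 + 30.26 = 46.2.

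So "This allow to achieve approximately 80% power to show superiority of reparixin vs standard of care" and the 46 events both reproduce. Under these assumptions about 2 of 48 patients are event-free at day 21, which leaves little room for a death before any component.

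**Effect on power.** Simulation of 32 reparixin and 16 control patients, 20,000 trials per row, final test at p < 0.024 without the interim, death as an independent competing time. The death risks are assumptions: 21-day risk in the absence of a component, reparixin/control.

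| Medians (days), reparixin vs control | Death risk | Censored deaths | Power, death censored | Power, death counted | Trials passing only with death censored |
|---|---|---|---|---|---|
| 5 vs 2 (SAP) | 0/0 | 0 | 0.83 | 0.83 | 0% |
| 5 vs 2 | 10%/10% | 1.3 | 0.82 | 0.81 | 2% |
| 5 vs 2 | 20%/20% | 2.7 | 0.81 | 0.79 | 4% |
| 5 vs 2 | 30%/10% | 3.6 | 0.81 | 0.74 | 8% |
| 25 vs 10 (assumed) | 10%/10% | 3.3 | 0.64 | 0.59 | 8% |
| 25 vs 10 (assumed) | 30%/10% | 8.3 | 0.63 | 0.30 | 32% |

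**Effect on false superiority.** Here total failure (component or death) is identical in the two arms, with an assumed 4-day median. A stated share of failures are deaths with no component recorded, so they replace component events. Same sample sizes and threshold, 20,000 trials per row.

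| Share, reparixin/control | Death censored | Death counted |
|---|---|---|
| 0/0 | 3.2% | 3.2% |
| 10%/0 | 6.3% | 3.4% |
| 20%/0 | 10.7% | 3.1% |
| 20%/10% | 6.5% | 3.4% |
| 30%/10% | 11.9% | 3.3% |
| 10%/10% | 3.2% | 3.4% |
| 0/10% | 1.7% | about 3% |
| 0/20% | 0.8% | about 3% |

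The no-death rate is 3.2% rather than 2.4% because the normal approximation to the log-rank is loose at 32 versus 16. The comparison to make is with 3.2%. A 10% share is about 3 of 32 reparixin patients; 20% is about 6 and 30% about 9.

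**Dependence on mechanism.** When death is independent of the component time, and component medians are equal (10 days in both arms, death risk 30%/10%), the four-component test stays at 3.3% and the five-component test falls to 1.3%. In that setting censoring does not inflate the error; it hides the excess deaths from the test. The inflation in the second table needs deaths that replace component events.

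**The case against.** The strongest case on the other side has four parts.

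- **The composite is broader than it looks.** A ward patient who gets no ICU bed can still be an event through PaO2/FiO2 worsening or rescue eligibility. This stands, and it limits the gap to deaths with none of the four components on record.
- **Deaths are seen elsewhere.** The DMC reviews safety at the end of phase 2 (SAP 4.6), deaths are tabulated (SAP 8.1), and phase 2 results go to the competent authority before phase 3 (SAP 4.7). This also stands as a separate safeguard. None of it changes the efficacy test that opens phase 3.
- **The size is chosen.** Equal shares leave the error unchanged, and more such deaths in controls lower it. This stands: the direction is unknown in advance.
- **Fixing one decision analysis in advance protects against choosing among results.** That is sound, but it argues for one pre-specified endpoint, and the version with death serves equally well.

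Three stronger readings are tempting and not supported. A reader might infer that any death without ICU, intubation or rescue is censored, but this overlooks the PaO2/FiO2 component. A reader might say that death counts as success, but censoring removes the patient from the risk set. A reader might say that a phase 2 pass driven by censored deaths leads to a false efficacy claim. SAP 7.1.1 calls phase 2 superiority preliminary and requires both nulls to be rejected, and the phase 3 endpoint counts death.

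**Conclusion.** The point holds as a cheap improvement to the design. No figure in the documents is shown to be wrong. A death before any of the four components is censored as event-free, and the pre-specified analysis that counts it cannot affect the decision to proceed.

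Under the SAP's own assumptions, with about 46 of 48 patients having an event and equal pre-event death risks of 10–20%, the effect is 1–2 points of power. It becomes material if the composite is slower than planned, or if unrecorded-component deaths are commoner on reparixin: phase 2 false superiority goes from about 3% to about 6% at 10% versus 0%, and to about 11% at 20% versus 0%. With the imbalance reversed it drops below 3%. All death shares are assumptions, and the inflation also assumes that these deaths replace component events. What is at risk is a wrongly opened phase 3.

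**What to change.** By protocol and SAP amendment, before any comparison by arm and before database lock:

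- Make the modified phase 2 composite in SAP Table 7 (components 1 to 5, including death) the phase 2 primary endpoint in SAP 3.5.1 and 7.1.1.1 and in protocol sections 3 and 9.4.2.1. Conform the protocol summary and section 9.1.
- Keep the four-component version as the sensitivity analysis.
- Apply the SAP Table 4 boundaries and the decision in 7.1.3.1 to the version with death.
- In Table 7, change the rule for setting the modified composite to No from components 1–4 to components 1–5. Death is already caught by the preceding Yes rule, so this is a correction of wording.

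The 46-event target does not change, since adding death can only add events. The derivation exists and Table 7 already takes the date of death from the death report form. The cost is a change of primary endpoint in an open-label trial, in a SAP dated seven months after the protocol version it cites. The change must be declared with its reason and made by people who have not seen results by arm. The documents do not say whether the phase 2 interim has taken place; if it has, the amendment should state who had seen its results.
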